1.2 Objectives

1) to assess and compare left atrial phasic volumes and function (as measured by ejection fraction and strain) at rest and during submaximal exercise in middle-aged endurance trained athletes with AF and age-matched healthy endurance trained athletes without AF.

2) to compare atrial electromechanical delay (AEMD) in middle aged endurance-trained athletes with AF to age-matched healthy non-AF endurance trained athletes. An exploratory objective will be to determine whether there is a correlation between P-wave duration and AEMD.

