1.3 Hypotheses

1) It is expected that left atrial strain will be impaired in athletes with AF compared to athletes without AF at both rest and during submaximal exercise- though impairments will be more pronounced during submaximal exercise. Specifically, it is hypothesized that left atrial (LA) reservoir function will be reduced in athletes with AF, as it is a strong predictor for AF.

2) It is expected that despite similar left atrial size, athletes with AF will have significantly prolonged AEMD compared to age-matched athletes without AF.

Additionally, it is hypothesized that P wave duration and AEMD will be correlated, suggesting AEMD may be a sensitive and precise measure for atrial fibrosis.

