2.4 Methods

General Procedures

All participants will be assessed at the same time of day. Participants will be asked to abstain from exercise on the day before and the day of each study visit.

Visit One: Participant Screening/Consent/ Graded Exercise Testing /

Echocardiography

The first visit will take place at the Heart Health Laboratory. Prior to attending the first visit, participants will have received consent forms and a 2-week Exercise Diary through email. Participants will complete consent form and have the opportunity to ask questions as needed upon their first visit, as well as return the 2-week Exercise Diary. Participants will be then familiarized with the procedures of the study. Participants will undergo basic anthropometric assessment to determine body mass (weight and height) and resting blood pressure. Following this, participants will be fitted with a 12-lead ECG and proceed to complete resting and submaximal exercise echocardiography, performed by a trained sonographer. Emphasis will be on left atrial volume, phasic function and AEMD. Exercise will be on a semi-recumbent cycle ergometer designed for stress echocardiography (Ergoline 1200EL). Imaging will be performed at rest, followed by a two-minute warm up. Participants will then cycle at 100 bpm for 5 minutes and at 130 bpm for 5 minutes; imaging will be initiated 2 minutes into each stage. During a 30-min rest period, participants will complete a Lifetime Physical Activity Questionnaire

Participants will then proceed to have a maximal cardiopulmonary exercise treadmill test with a HR monitor (Polar V800).

Visit Two: Resting Signal Averaged ECG/ Cardiac Magnetic Resonance Imaging/Holter Monitor

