2.7.2 Resting and Submaximal Echocardiography

Participants will undergo transthoracic echocardiography (GE E9 Imaging System) at the Heart Health Laboratory, provided the individual is in sinus rhythm. Imaging will be performed by a trained sonographer, and images will be obtained according to the criteria of the American society of echocardiography guidelines. Subjects will be initially placed in a supine position on a purpose-built imaging/cycle ergometer (Ergoline 1200E), for assessment of resting cardiac structure and function. During exercise, subjects will be repositioned to a 45 degree semi-upright position with minor left caudal tilt to optimize imaging. Cycle ergometry will be performed concurrent with echocardiography.

For all acquisitions, two-dimensional apical (two and four chamber view) and parasternal (long and short axis) imaging will be performed for dimensional and functional parameters of the atria and of the ventricles at a frame rate of 60-80 (fps). Volume and size measurements will be normalized to body surface area. Echocardiograph imaging will primarily be used for functional measures at rest and exercise; structural assessment of chambers will be determined using cMRI. Emphasis

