2.7.4 Cardiac Magnetic Resonance Imaging

All athletes with AF will undergo resting cardiac magnetic resonance imaging (cMRI) at St. Michael's hospital, following methods used for previous REB-approved study). MRI will be performed supine in a 3.0T scanner (Siemens MAGNETOM Skyra 3.0T with TIM and DOT technology); images will be obtained on end-expiration breath holds. Vertical long-axis cine images will be prescribed from axial scout images by aligning the left ventricular (LV) apex with the center of the mitral valve. From these LV long-axis images, the horizontal long-axis plane will be obtained by aligning the midpoint of the left ventricular apex and mitral valve. These pilot 4-chamber and 2-chamber views provide the reference images on which a stack of contiguous short-axis slices will be prescribed, covering the left atrium and left ventricle. Depending on the LV long-axis length, 8-12 contiguous slices will cover the entire left ventricle. Providing normal creatine levels are verified (see above), delayed enhancement MRI will be acquired 10 minutes after contrast agent injection of gadolinium (0.1 mmol/kg body weight, Multihance, Bracco Diagnostic Inc, Princeton, NJ) (MRI contrast agent does not contain iodine and does not damage the kidneys. Subjects refusing gadolinium will still be studied. Imaging will be used for cardiac structure and volumetric assessments of the

atria and ventricles (max and min volume, EDV and ESV). All data analysis will be performed using CMR42 (Circle Imaging, Calgary, Canada). End-diastolic frames are defined as the image with the largest ventricular volume in each series, and end-systolic as the image with the smallest volume. Endocardial and epicardial borders on these frames will be manually traced. From this data, LV and RV ejection fraction, end diastolic/end systolic and stroke volume indices will be calculated. Manual tracing of endocardial borders of short-axis images at atrial end-diastole and atrial end-systole will allow for calculation of LA end-diastolic volume and end-systolic volume.

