2.8 Data Analysis

All variables will be expressed as mean and standard deviation. Differences in outcome measures (AEMD, atrial phasic function, atrial dimensions) will be assessed using a series of independent t-tests between the athletes with AF and athletes without AF. A 2-way repeated measures analysis of variance (ANOVA) will be used to compare resting and exercise values between and within groups. Covariates will be included when appropriate, including age, years since AF diagnosis, and number of AF episodes. Atrial size and relation to ECG parameters may be studied for correlational analyses.

Significance will be set at $p < 0.05$. Analysis will be performed using SPSS software.

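### Rest is imaged supine and exercise at 45 degrees, so the planned within-group rest-to-exercise change mixes posture with exercise

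*Combined protocol and SAP*

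**What the plan says.** **Resting posture (section 2.7.2).** "Subjects will be initially placed in a supine position" for the resting assessment of cardiac structure and function.

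**Exercise posture (section 2.7.2).** "During exercise, subjects will be repositioned to a 45 degree semi-upright position with minor left caudal tilt to optimize imaging".

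**Order of imaging (section 2.4, Visit One).** "Imaging will be performed at rest, followed by a two-minute warm up". Participants then cycle for 5 minutes at 100 bpm and 5 minutes at 130 bpm, and "imaging will be initiated 2 minutes into each stage". Neither section describes a second resting acquisition after the change of position.

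**Analysis (section 2.8).** "A 2-way repeated measures analysis of variance (ANOVA) will be used to compare resting and exercise values between and within groups". The covariates named there are age, years since AF diagnosis and number of AF episodes. Posture is not mentioned.

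**What the comparison is for.** Objective 1 (section 1.2) concerns left atrial volumes and function "at rest and during submaximal exercise in middle-aged endurance trained athletes with AF" against athletes without AF. Hypothesis 1 (section 1.3) expects impaired left atrial strain in AF at rest and during exercise, "though impairments will be more pronounced during submaximal exercise".

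**The concern.** Each participant changes posture at the same point as he passes from rest to exercise. In the rest-versus-exercise contrast, posture and exercise are therefore completely confounded. A covariate cannot separate them, because posture does not vary within a condition. More participants would not help either, since every one of them follows the same sequence.

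At stake is the reading of the within-group part of the ANOVA. A significant change in reservoir strain from rest to 100 or 130 bpm would naturally be described as the atrial response to exercise, and the design does not support that description. The missing image cannot be recovered once the session is over.

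**Working it through.** **1. The plan's own figure, to see whether posture enters it.** Section 2.2 gives a between-group difference in reservoir strain of 6.49 with SD 5.2, alpha 0.05 and power 0.8. With the two-sided normal formula:

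n per group = 2 × (1.96 + 0.842)² × 5.2² / 6.49² = 2 × 7.85 × 27.04 / 42.12 = 10.1, rounded up to 11.

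This matches the stated 11 (solving with the t distribution gives 11.12). The inputs are a difference between two groups and its SD. No rest-to-exercise change is used, so the calculation does not depend on posture. The AEMD calculation in the same section is also between-group.

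**2. The acquisitions, side by side.**

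| Acquisition | Posture | Source |
|---|---|---|
| Rest, before warm-up | Supine | 2.7.2 for posture, 2.4 for order |
| 100 bpm stage | 45 degrees semi-upright | 2.7.2, 2.4 |
| 130 bpm stage | 45 degrees semi-upright | 2.7.2, 2.4 |
| Rest at 45 degrees | Not specified | – |

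**3. What each contrast estimates.** For group g, let R_g be the mean at supine rest, P_g the effect of moving from supine to 45 degrees while still at rest, and E_gs the further effect of exercise at stage s in the 45-degree position. The observed means are R_g at rest and R_g + P_g + E_gs at stage s.

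- Within-group change, rest to stage s: P_g + E_gs. Two unknowns, one contrast.
- Within-group change, 100 to 130 bpm: E_g,130 − E_g,100. Posture cancels, but there is no rest level in it.
- AF versus non-AF at rest: R_AF − R_H. Both groups are supine.
- AF versus non-AF at stage s: both groups are at 45 degrees, so like is compared with like.
- Group by stage (difference in change): (P_AF − P_H) + (E_AF,s − E_H,s). Posture cancels if P_AF = P_H.

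With a resting image at 45 degrees, R_g + P_g is observed directly. The within-group change becomes E_gs, and the difference in change becomes E_AF,s − E_H,s, whether or not posture acts alike in the two groups.

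**4. Illustration.** All values are assumed, in strain points, and none comes from the documents. Take an exercise effect of +2 in athletes with AF and +5 in those without, and a posture effect common to both groups.

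| Assumed posture effect | Observed change, AF | Observed change, non-AF | Difference in change |
|---|---|---|---|
| −3 | 2 − 3 = −1 | 5 − 3 = +2 | −3 |
| 0 | +2 | +5 | −3 |
| +3 | 2 + 3 = +5 | 5 + 3 = +8 | −3 |

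The within-group change moves point for point with posture and can change sign. The difference between groups does not move.

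**The case against.** The strongest reply is that the affected contrast is not what the study is about. Objective 1, hypothesis 1 and the sample size all concern athletes with AF against athletes without. The within-group change enters only through the wording of the ANOVA in section 2.8. Both groups go through the same sequence of positions, so a posture effect common to both leaves the group comparisons unbiased. This stands, and it limits the point to the within-group change.

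It can also be said that the problem is one of labelling, since no section commits to calling the change a response to exercise alone. That is fair as far as it goes, and accurate labelling is offered below as the fallback. But section 2.8 does plan the within-group comparison, and as designed it cannot show what exercise does to atrial function.

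Section 2.4 gives no posture for the resting image and refers to a semi-recumbent ergometer, so one might suppose that rest was also imaged semi-upright. Section 2.7.2 settles this: rest is supine. The stated purpose of the 45-degree position, better images, explains the exercise posture but not the lack of a matched resting image.

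Finally, adding a second resting image has a drawback. The resting part of hypothesis 1 would be tested on supine images and the exercise part against 45-degree rest. This is a real mismatch. It is met by also reporting the group difference at 45-degree rest.

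**Conclusion.** The point holds for the within-group rest-to-exercise change, which combines posture and exercise in a way that the planned data cannot separate. This follows from the described sequence of acquisitions and needs no numerical assumption. The documents give no posture effect on atrial strain or volumes, so the size of the distortion is unknown and none is claimed.

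A reader might infer more: that the AF versus non-AF comparisons are biased, that hypothesis 1 cannot be tested, or that the sample size is wrong. The documents do not support this. Group comparisons at rest and at each exercise stage are made in a common posture, and the sample size uses only between-group figures. The group-by-stage interaction, which bears on whether impairment is greater during exercise, would be distorted only if the posture response differed between the groups. The documents neither support nor exclude that.

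**What to change.** Add to sections 2.4 and 2.7.2 a brief set of resting left atrial loops at 45 degrees, taken just before the warm-up. Then state in section 2.8:

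- the 45-degree resting value is the rest level in the repeated measures ANOVA, for both the within-group change and the group-by-stage interaction;
- the supine images remain the pre-specified resting comparison of athletes with and without AF;
- the group difference at 45-degree rest is also reported, so that both parts of hypothesis 1 can be read against the same rest level.

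The cost is a few minutes of extra imaging for each of the 34 planned participants (17 per group), in the same session with the same sonographer and ergometer. The few minutes are an assumption, as the documents give no figure. The change also creates two resting values, which is why the plan must say in advance which one answers which question.

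If the image is not added, report the contrast as *supine rest versus semi-upright exercise* and do not interpret it as a response to exercise alone. That costs only wording.

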will be on left atrial reservoir function, as this parameter has provided robust insight into AF-associated impairment even in the presence of normal LA size. Left atrial volumes will be measured at different time points of the cardiac cycle. Atrial maximal volume (LA max) will be measured at the end of ventricular systole, prior to the opening of the mitral valve; atrial pre-A volume (LA PRE-A) will be measured prior to onset of atrial contraction (beginning of P wave); atrial minimal volume (LA min) will be measured at the closure of the mitral valve. Accordingly, LA phasic volumes and emptying fractions will be calculated. Left and right ventricular volumes and ejection fraction will be calculated by the modified bi-plane Simpson's method. Images for LA strain will be obtained using Speckle Tracking echo. Strain measures will include global longitudinal strain, peak atrial longitudinal strain, and atrial phasic strain (reservoir: during ventricular systole, conduit: during early ventricular diastole and booster: during late ventricular diastole). Left ventricular strain during ventricular systole, early diastole and late diastole will also be measured. Pulsed-wave Doppler interrogation of transmitral flow will be obtained at the septal and lateral mitral annulus to determine flow velocities during early (E) and late (A) diastole, as well as the E/A ratio. Tissue Doppler imaging will also be performed at the septal and lateral mitral annulus to determine myocardial systolic (Sm), early diastolic (Em) and late diastolic (Am) velocities. Care will be taken to minimize gain and all analyses of DTI and Doppler flow patterns will be conducted according to current ASE guidelines⁸⁴⁻⁸⁶. The collection of these images will allow us to calculate intracardiac volumes and indices of diastolic and systolic function.

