2.7.3 Atrial Electromechanical Delay

Tissue Doppler Echocardiography will be performed by transducer frequencies of 3-4MHz, adjusting the spectral pulsed Doppler signal filters until a Nyquist limit of 15-20cm/s and using the minimal optimal gain. The monitor sweep speed will be set to 50-100mm/s to optimize the spectral delay of myocardial velocities. In apical 4-chamber view, the pulsed Doppler sample volume will be placed at the lateral and septal sides of the mitral annulus and the right-ventricular (RV) tricuspid annulus to obtain tissue Doppler velocities. The time intervals from the onset of the P wave (ECG) to the beginning of the Am wave (on echo) will be measured from the lateral mitral annulus (lateral PA), septal mitral annulus (septal PA), and RV tricuspid annulus (tricuspid PA). The timing of mechanical activation of each sample point is dependent on the distances of each point to the sinoatrial node (SA). Accordingly, the RV tricuspid annulus is the earliest (closest) and the lateral mitral annulus is the latest (farthest) point to be activated by impulses from the SA node. The difference between any two reference points reflects the mechanical delay between these two points Inter-AEMD will be defined as the difference between the lateral PA and tricuspid PA, intra-right AEMD will be defined as the difference between the septal PA and tricuspid PA, and intra-left AEMD will be defined as the difference between the lateral PA and septal PA.

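### Two secondary echo rules in section 2.7.2 are wrong as written: transmitral flow is assigned to the tissue-Doppler sites, and right ventricular volumes to a biplane method whose apical views show that chamber only once

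*Combined protocol and SAP*

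**What the plan says.** **Transmitral flow.** Section 2.7.2 states: "Pulsed-wave Doppler interrogation of transmitral flow will be obtained at the septal and lateral mitral annulus", and gives the purpose as "to determine flow velocities during early (E) and late (A) diastole, as well as the E/A ratio". The sentence that follows reads: "Tissue Doppler imaging will also be performed at the septal and lateral mitral annulus", this time for the myocardial velocities Sm, Em and Am. Section 2.7.3, on atrial electromechanical delay, again uses these sites for tissue velocities: "the pulsed Doppler sample volume will be placed at the lateral and septal sides of the mitral annulus". Section 2.7.2 refers to the ASE guidelines twice, once for obtaining the images and once for analysis: "all analyses of DTI and Doppler flow patterns will be conducted according to current ASE guidelines".

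**Right ventricle.** Section 2.7.2 gives one rule for both ventricles: "Left and right ventricular volumes and ejection fraction will be calculated by the modified bi-plane" Simpson's method. The views it lists are: "two-dimensional apical (two and four chamber view) and parasternal (long and short axis) imaging will be performed". It does not say which views form the pair for the right ventricle. The section also leaves chamber structure to cMRI, and section 2.7.4 says of the resting cMRI: "From this data, LV and RV ejection fraction, end diastolic/end systolic and stroke volume indices will be calculated".

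**The concern.** The first rule gives a blood-flow measurement the position of a wall-motion measurement. Transmitral inflow is a single stream, so it needs one sample position within that stream, and none is stated anywhere. The two sites that are stated lie at the edges of the inflow. What is recorded there depends on exactly where the sample volume sits, and the rule yields two sets of E, A and E/A at each stage. Neither section 2.7.2 nor section 2.8 says whether to use the septal set, the lateral set or their average.

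The second rule asks for a biplane volume of a chamber that appears in only one of the two apical views listed.

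At stake are whether E/A is standardised and comparable between the athletes with and without AF, and whether an echo right ventricular volume or ejection fraction can be produced as described. A flow signal recorded at the wrong position cannot be repaired at analysis, so the wording matters before imaging starts.

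**Working it through.** The plan gives no figure for this point, so the check compares the texts and counts what is exposed.

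**1. Sites by measurement**

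| Measurement | Quantity | Sites stated | Section |
|---|---|---|---|
| Pulsed-wave Doppler, transmitral | Blood flow: E, A, E/A | Septal and lateral mitral annulus | 2.7.2 |
| Tissue Doppler | Wall velocity: Sm, Em, Am | Septal and lateral mitral annulus | 2.7.2, next sentence |
| Tissue Doppler for AEMD | Time from P wave to Am | Septal and lateral mitral annulus, tricuspid annulus | 2.7.3 |

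The last two rows are consistent with each other. The first row gives the same sites to a different physical quantity, which suggests that the site wording was carried across from tissue Doppler.

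**2. Right ventricle by view**

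| View listed in 2.7.2 | Right ventricle shown? |
|---|---|
| Apical four-chamber | Yes |
| Apical two-chamber | No |
| Parasternal long axis | In part |
| Parasternal short axis | In part |

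The right-hand column is general imaging anatomy and is not stated in the documents. A biplane volume needs the cavity in two paired planes. The apical pair supplies one for the right ventricle. The plan names no alternative pair, and the parasternal views do not add a second full long-axis plane.

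**3. How much is exposed**

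- Planned participants (2.2): 17 per group, so 17 × 2 = 34.
- Imaging stages (2.4): rest, 100 bpm and 130 bpm, so 3.
- Participant-stages: 34 × 3 = 102. For transmitral Doppler this is an upper limit. The wording in 2.7.2 that covers every acquisition refers to two-dimensional imaging, and Doppler is not explicitly required at each stage.
- E/A values if both annular sites are recorded every time: 102 × 2 = 204, for 102 inflows.
- Right ventricle: the 34 resting assessments are also covered by cMRI. The exercise assessments, 34 × 2 = 68, are not, because cMRI is done only at rest.

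**4. Link to the main analyses**

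The primary outcomes in 2.2 are left atrial reservoir strain and AEMD. The sample size rests on a strain difference of 6.49 (SD 5.2) and an AEMD difference of 7.7 ms (SD 7). Neither E/A nor any right ventricular measure enters these figures. The outcomes that 2.8 names for group comparison are AEMD, atrial phasic function and atrial dimensions. E/A and right ventricular measures could come in only through the general comparison of resting with exercise values in 2.8, or through the systolic and diastolic indices mentioned at the end of 2.7.2.

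**The case against.** The best defence is that a trained sonographer working to ASE guidelines, which the plan cites for both acquisition and analysis, would not follow the flow sentence literally. On that view it is a drafting slip with no effect on the data. In part this stands: practice may well be sound, and the guideline text is not in the documents, so its conflict with the stated site cannot be checked line by line. It does not cure the wording. A general reference beside an explicit site leaves the operator to decide which one governs.

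A reader might go further than the documents allow in four ways.

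- **That the E and A values would be invalid or unobtainable.** Sampling at annular level can still record inflow. The supportable statement is that the values would depend on position and would not be standardised.
- **That no listed view except the four-chamber shows the right ventricle.** The parasternal views are also listed and show parts of it. The gap concerns the apical pair and the absence of any named alternative.
- **That the main conclusions are at risk.** Neither primary outcome uses these measures, nor does any outcome named in 2.8.
- **That these indices are needed to separate atrial from ventricular dysfunction.** Section 1.1 mentions left ventricular function as part of the rationale, but no section gives E/A or right ventricular volumes that role.

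It is also fair to say that resting right ventricular values already come from cMRI, so the second rule matters mainly for exercise, where no objective depends on it.

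**Conclusion.** Both rules are wrong as written, not merely short of detail. The flow rule names a specific site that the plan otherwise reserves for wall motion, and it creates duplicate values with no rule for choosing between them. The right ventricular rule cannot be carried out with the apical pair listed, and no other pair is given.

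The consequence is limited. It covers secondary diastolic indices (up to 102 participant-stages) and echo right ventricular volumes and ejection fraction, chiefly the 68 exercise participant-stages that have no cMRI counterpart. The primary outcomes and the sample size stand. The direction and size of any E/A error cannot be derived from the documents.

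The conclusion rests on two pieces of general imaging knowledge: that transmitral inflow is one stream needing one sample position, and that the apical two-chamber view does not contain the right ventricle.

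**What to change.** Amend two sentences in section 2.7.2.

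1. **Flow.** State that pulsed-wave Doppler of transmitral inflow is recorded in the apical four-chamber view with a single sample position at the mitral leaflet tips. Keep the septal and lateral annulus for tissue Doppler only. State the stages at which transmitral Doppler is recorded.
2. **Ventricular volumes.** Limit modified biplane Simpson to the left heart. State that resting right ventricular volumes and ejection fraction come from cMRI, as 2.7.4 already provides. If an exercise right ventricular measure is wanted, name a single-plane measure from the four-chamber view. This is optional.

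The cost is a wording change, with no added imaging. There are two downsides. There would be no exercise right ventricular volumes. The resting right ventricular comparison would set new scans in the AF group against control scans from the earlier study (2.0 and 2.4), taken at an interval the documents do not give, and this should be acknowledged when the results are reported.
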